### **9.2.1 Target Population**

Patients are eligible for observation in this cohort if the following applies:

- Treatment-naïve or -experienced adult male or female patients (age  $\geq 18$  yrs) with confirmed CHC, genotype 1 or 4, receiving combination therapy with the interferon-free ABBVIE REGIMEN  $\pm$  RBV according to standard of care and in line with the current local label
- If RBV is co-administered with the ABBVIE REGIMEN, it has been prescribed in line with the current local label (with special attention to contraception requirements and contraindication during pregnancy)
- Patients must be able to speak and understand the Dutch language at such a level that they can understand and sign the informed consent and be able to understand and complete the questionnaires without any external help
- Patients must voluntarily sign and date informed consent prior to inclusion into the study

Patients are not eligible for observation in this cohort if the following applies:

- Patients participating or intending to participate in a concurrent interventional therapeutic trial
- Patients who are unable to complete the questionnaires due to cognitive impairment or lack of any kind of cognitive competence, as to be judged by the healthcare professional who is treating the patient
- Patients who are unable to complete the questionnaires due to language incompetence
- Patients who are unable to voluntarily sign and date the informed consent
- Patients included for treatment who do not meet the treatment criteria as described in the current label

---

Confidential Information

No use or disclose outside AbbVie is permitted without prior written authorization from AbbVie

The Netherlands v 1.4 (26 March 2018). Protocol based on AbbVie shell protocol version 3.0 (22 April 2015) Page 23 of 65

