### **9.4.1.1 Inclusion Documentation**

Inclusion:

Patients will be included only after the physician and the patient have decided to treat chronic HCV with paritaprevir/r and ombitasvir +/- dasabuvir +/- ribavirine. To guarantee independence of prescription choice of the HCP, a nurse practitioner will check if a newly prescribed patient might be eligible for the study and if so, may inform the patient about participation in the observational study.

Patients can be enrolled in the PMOS during the first 4 weeks of treatment, enabling the nurse practitioner to search eligible newly prescribed patients also from medical records.

After the patient has been found eligible and after the informed consent has been signed, the following will be documented if available:

- Demographic information
  - Interleukin 28B (IL28B) genotypes
- CHC disease characteristics
  - Year of diagnosis and mode of infection
  - Stage of liver fibrosis/cirrhosis (Annex 4)
- CHC treatment history
  - Naïve or experienced
  - If experienced, most recent prior therapy and outcome
- Relevant medical history, co-morbidities and co-infections
- Concomitant medication, see 9.4.1.5
- ABBVIE REGIMEN ± RBV

- Laboratory data

Key clinical chemistry	Remarks
▪ ALT (alanine-aminotransferase)	including upper limit of normal (ULN),
▪ AST (aspartate-aminotransferase)	including ULN, AST to platelet ratio index (APRI) and Fibrosis-4 Score/Index (FIB-4)* will be calculated
▪ γ-GT (gamma-glutamyltransferase)	
▪ Total bilirubin	
▪ Albumin	
▪ Creatinine	creatinine clearance # will be calculated
▪ AFP	
Key hematology	
▪ Hb (Hemoglobin)	
▪ Platelets	
▪ Prothrombin time	or international normalized ratio (INR)
Virology	
▪ HCV genotype and subtype	
▪ HCV RNA	quantitative/ qualitative HCV RNA by polymerase chain reaction (PCR) test, see 9.4.1.4
HIV-infected patients only	
▪ CD 4 count (cluster of differentiation 4)	most recent assessment
▪ HIV RNA	in copies/mL

\*derived from patient's age, ALT, AST and platelets

#by Cockcroft-Gault-Formula based on creatinine, gender, age and weight

- Patient questionnaires, see Table 2 and 9.4.1.6
- Treatment related health care resource utilization

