4.2 Statistical and Analytical Methods

4.2.1 Analysis Populations and Analysis Groups

Population of Patients Enrolled [EP]

The population of patients enrolled comprises all patients who voluntarily sign and date an informed consent prior to inclusion into the study and data were captured in the eCRF.

Target Population [TP]

Patients will be included if the following applies:

- Age at least 18 years
- Confirmed CHC with genotype 1 and/or 4 only, receiving combination therapy with the interferon-free ABBVIE REGIMEN \pm RBV. The prescribed ABBVIE REGIMEN needs to be known.
- Have voluntarily signed and dated an informed consent prior to inclusion into the study
- Must not be participating or intending to participate in a concurrent interventional therapeutic trial

Core Population [CP]

The core population is defined as all patients of the target population (TP) (definition see above), who are adequately treated according to the standard of care and within local label recommendations for their specific disease characteristics (cirrhotic status, genotype). The following patients will be excluded from the CP:

- Patients with unknown fibrosis status
- Cirrhotic patients with genotype 1a not receiving ribavirin
- Patients with genotype 1 for whom 2DAA instead of 3DAA is prescribed
- Patients with genotype 4 not receiving RBV

Non-Core Population [NCP]

Patients in the TP who are not in the CP.

Core Population with Sufficient Follow-up [CPSFU {12, 24}]

In addition, the core population with sufficient follow-up data regarding SVR12 or SVR24, respectively, is defined as all CP patients,

- who have evaluable HCV RNA data ≥ 70 days or >126 days, respectively, after the last actual dose of the ABBVIE REGIMEN
- or a HCV RNA value ≥ 50 IU/mL at the last measurement post-baseline
- or had HCV RNA <50 IU/mL at the last measurement post-baseline, but no HCV RNA measurement ≥ 70 days or >126 days, respectively, after the last actual dose of the ABBVIE REGIMEN due to reasons related to safety (e.g. dropped out due to adverse event) or virologic failure (e.g. virologic failure such as relapse is reported in the electronic case report form (eCRF) but date and value of the corresponding HCV RNA test is missing).

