This means only (1) patients who had virological response at their last on-treatment or post-treatment measurement, but had no post-treatment HCV RNA measurements ≥ 70 days or >126 days, respectively, for reasons not related to safety or effectiveness (e.g. lost-to-follow-up or patient not willing to perform an additional HCV RNA test ≥ 70 days or >126 days post-treatment, respectively) and (2) patients who had no post-baseline HCV RNA measurements for reasons not related to safety or effectiveness, and (3) patients with missing end of treatment date for reasons not related to safety or effectiveness, will be excluded from this analysis.

Safety population [SP]

The safety population is defined as all enrolled patients who received at least one dose of the ABBVIE REGIMEN. The prescribed ABBVIE REGIMEN needs to be known.

EP and TP analysis groups

The EP/TP analysis groups are defined according to the patient's fibrosis status and genotype/subtype and standard summaries are structured as follows:

- Total (regardless of cirrhosis status)
 - (1) Total (regardless of genotype)
 - (2) G1 (Total)
 - (3) G1a (including mixed G1 subtypes and patients with G1 unknown subtype)
 - (4) G1b
 - (5) G4 (non-G1)
 - (6) Other/unknown genotype (*only for EP*)
- Patients with cirrhosis
 - (7) Total (regardless of genotype)
 - (8) G1 (Total)
 - (9) G1a (including mixed G1 subtypes and patients with unknown G1 subtype)
 - (10) G1b
 - (11) G4 (non-G1)
 - (12) Other/unknown genotype (*only for EP*)
- Patients without cirrhosis
 - (13) Total (regardless of genotype)
 - (14) G1 (Total)
 - (15) G1a (including mixed G1 subtypes and patients with unknown G1 subtype)
 - (16) G1b
 - (17) G4 (non-G1)
 - (18) Other/unknown genotype (*only for EP*)
- Patients with unknown fibrosis status
 - (19) Total (regardless of genotype)
 - (20) G1 (Total)
 - (21) G1a (including mixed subtypes and patients with unknown subtype)
 - (22) G1b
 - (23) G4 (non-G1)
 - (24) Other/unknown genotype (*only for EP*)

(HCV genotypes will be combined as follows: G1 [total], G1a*, G1b, G4 [non-G1]. * includes mixed or other G1 subtypes and patients with unknown G1 subtypes.

Most recent stage of liver fibrosis will be categorized as follows: No cirrhosis/Transition to cirrhosis, Cirrhosis. Only one method should be selected by the physicians to report stage of fibrosis. Nevertheless, if there are multiple answers the following priority will be used:

1. Biopsy,
2. Non-invasive,
3. Clinical/best guess.

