4.2.7 Analyses of the Objectives

4.2.7.1 Primary Effectiveness Variable

The primary objective of this study is to estimate the SVR12 rates in HCV patients treated according to the ABBVIE regimen.

Therefore the simple percentage of patients achieving SVR12 (for definition see section 4.1.1) will be calculated and a two-sided 95% confidence interval (CI) of the percentage will be computed based on the Wilson's Score method.

The primary effectiveness analysis on clinical outcomes will be performed on all patients in the CP stratified by genotype and cirrhosis status and overall.

In the framework of sensitivity analyses the primary analyses will be repeated for the CPSFU. Furthermore, the SVR12 rates will be also determined for all patients of the NCP.

An overview of Tables is given in Table 7.

The layouts of the tables mentioned above are provided in Part II of the SAP (Table Shells).

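### Enrolment up to 4 weeks after treatment start can miss early stoppers among late-enrolled patients, and the SAP neither measures nor examines this selection

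*Protocol*

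**What the plan says.** Protocol 9.4.1.1 describes a nurse practitioner checking newly prescribed patients after the treatment decision, and then widens the window: "Patients can be enrolled in the PMOS during the first 4 weeks of treatment, enabling the nurse practitioner to search eligible newly prescribed patients", with medical records named as a source.

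Protocol 9.2.1 describes the eligible patient as "receiving combination therapy with the interferon-free ABBVIE REGIMEN", and adds: "Patients must voluntarily sign and date informed consent prior to inclusion into the study".

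SAP 4.2.1 builds its analysis sets on that consent. For the EP: "The population of patients enrolled comprises all patients who voluntarily sign and date an informed consent prior to inclusion into the study". For the SP: "The safety population is defined as all enrolled patients who received at least one dose of the ABBVIE REGIMEN". The TP also requires consent, and the CP, NCP and CPSFU are subsets of the TP.

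The primary analysis (SAP 4.2.7.1) uses the CP: "The primary effectiveness analysis on clinical outcomes will be performed on all patients in the CP stratified by genotype and cirrhosis status and overall". Its precision is expressed as follows: "a two-sided 95% confidence interval (CI) of the percentage will be computed based on the Wilson's Score method". Early termination is a simple frequency in the CP and SP (SAP 4.2.5), and TEAEs are summarised in the SP (SAP 4.2.8.3).

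Neither document asks for consecutive enrolment, a log of all patients who started treatment, a table of enrolment timing, or an analysis restricted to patients enrolled by the first dose. On bias in the SVR rate, Protocol 9.9 names only missing follow-up HCV RNA, which it says leads to underestimation.

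**The concern.** This is left truncation. A patient enrolled in week 3 or 4 had to remain available, alive and ordinarily still on treatment until then. A patient who started at the same time and stopped in week 2, before anyone approached them, would usually not enter. That patient appears in no analysis set, so neither the missing-equals-failure rule nor the CPSFU sensitivity analysis can recover them.

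The outcome most exposed is premature discontinuation, including stopping for adverse events, because the missed patients are by definition events. SVR12 is exposed to the extent that missed patients would have been failures.

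The study exists to show how pivotal-trial results carry over to routine care. Protocol 7.1 motivates it by the experience with the first protease inhibitors, whose everyday tolerability fell short of the development trials in some subgroups. Selection on early tolerance would weaken that comparison, and nothing in the planned output would let a reader see whether it occurred.

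**Working it through.** The plan has no figure of its own to reproduce: the 50–55 patients are stated not to rest on statistical considerations. The check is therefore a sensitivity model.

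**Inputs from the documents**
- Enrolment is possible up to 4 weeks into treatment (Protocol 9.4.1.1).
- 50–55 patients are expected (Protocol 9.5, SAP 3.2).
- The interval is a two-sided 95% Wilson interval (SAP 4.2.7.1).
- Trial discontinuation is called low, without a number (Protocol 7.1).

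**Inputs assumed, because the documents give none**
- q = share of starters who stop before about week 4: 2% to 5%.
- f = share of starters due to be approached only at about week 4: 50%, with 25% as a variant.
- Every early stopper in share f is missed and would have been an SVR12 failure.
- l = later discontinuation among those who continue: 1%.
- Observed SVR12 of 51/53 = 96.2%.

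**SVR12**

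With p the SVR12 rate in continuers, true SVR12 = p(1−q) and observed SVR12 = p(1−q)/(1−qf). Hence true = observed × (1−qf), and bias = observed × qf.

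| q | f | Bias (points) | SVR12 in all starters | Missed per 53 enrolled, 53·qf/(1−qf) |
|---|---|---|---|---|
| 2% | 50% | 96.2 × 0.010 = 0.96 | 95.3% | 0.54 |
| 5% | 50% | 96.2 × 0.025 = 2.41 | 93.8% | 1.36 |
| 2% | 25% | 96.2 × 0.005 = 0.48 | 95.7% | 0.27 |
| 5% | 25% | 96.2 × 0.0125 = 1.20 | 95.0% | 0.67 |

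The rows with f = 25% also describe half the patients being approached late with approaches and stops spread evenly over the 4 weeks, because about half the stops then precede the approach. With f = 0 the bias is zero.

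**Discontinuation**

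True = q + (1−q)l; observed = [(1−f)q + (1−q)l]/(1−qf). With f = 50%:
- q = 2%: true 0.02 + 0.98 × 0.01 = 2.98%; observed (0.01 + 0.0098)/0.99 = 2.00%. About a third is lost (1 − 2.00/2.98 = 33%).
- q = 5%: true 0.05 + 0.95 × 0.01 = 5.95%; observed (0.025 + 0.0095)/0.975 = 3.54%. About two-fifths is lost (1 − 3.54/5.95 = 41%).

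**Comparison with sampling error**

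The Wilson interval is 87.7–99.0% at 53/55 and 86.5–98.9% at 48/50. Adding one missed early stopper as a failure to 53/55 gives 53/56 = 94.6% (85.4–98.2%); adding two gives 53/57 = 93.0% (83.3–97.2%). The shift in SVR12 lies well inside the interval. The interval describes sampling error only, however, and does not cover selection.

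**The case against.** The strongest case on the other side has five parts.

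1. **Late entry is a permission.** Protocol Table 2 places consent at baseline, the questionnaires are due before treatment starts (Protocol 9.3.2), and SAP 4.2.5 lists never having started treatment among the reasons for not completing the study, so some enrolment before the first dose is foreseen. This stands. A reader might infer that the whole cohort had already tolerated treatment; the documents do not support that, and the point applies only to patients enrolled after the first dose.

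2. **No rule excludes early stoppers.** No criterion mentions tolerability or early response, and the record search targets newly prescribed patients. This stands in part: the loss is a tendency arising from the requirement to be on the regimen and the need for consent. It is not a stated exclusion. That early HCV RNA results steer the choice of patients is possible, but no passage says so.

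3. **The timing of the analysis is not itself wrong.** SAP 4.2.7.1 names only a population and an interval. SVR12 is timed from the last dose, and discontinuation is a simple frequency. This stands. The defect lies in who enters the cohort.

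4. **The size rests on assumptions and could not change a decision.** The study is descriptive and has no threshold. This stands for SVR12. It is weaker for discontinuation, where one or two patients may be a large part of all events.

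5. **The net direction for SVR12 is open.** HCV RNA still missing after imputation counts as failure (Protocol 9.7.1, SAP 4.2.3), which lowers SVR12. This stands. A reader might infer that the reported SVR12 must be too high overall; the documents do not settle which bias dominates.

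**Conclusion.** The point holds in a limited form. Among patients enrolled after the first dose, those who stopped or died before being approached tend to be missed. Taken alone, this selection understates early discontinuation and AE-related stopping and raises SVR12. No analysis set or sensitivity analysis in the plan detects or removes it.

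The size cannot be read from the documents. Under the stated assumptions (half approached at about week 4, 2–5% stopping earlier, all such patients in the late-approached half missed and counted as failures), SVR12 is about 1.0–2.4 points too high. It is about 0.5–1.2 points if approaches and stops are spread evenly over the window, and zero if everyone consents by day 1. The discontinuation rate is affected more in relative terms, by about a third to two-fifths under the same assumptions with 1% stopping later. The net SVR12 bias, after missing-equals-failure, is not established.

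This warrants a low-cost addition to the analysis. It does not invalidate the primary estimate.

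**What to change.** - **SAP 4.2.5:** tabulate the interval from first dose to consent. First confirm that the consent date is in the database, since the items listed in Protocol 9.4.1.1 do not name it; otherwise take it from the dated consent form.
- **SAP 4.2.7.1, 4.2.5 and 4.2.8.3:** repeat the SVR12, premature-discontinuation and TEAE summaries for patients who consented on or before study day 1. These estimates are free of this selection.
- **Protocol 9.9:** name this selection beside the missing-data bias, and say that the two act on SVR12 in opposite directions.
- **Reporting:** if a relevant share enrolled late, word the discontinuation and SVR12 conclusions as conditional on still being on treatment at enrolment.
- **Optional:** a discontinuation estimate with delayed entry at consent. With so few events it would be imprecise.

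The cost is SAP wording, one table, one extra set of summaries and possibly retrieval of consent dates. The enrolment window need not change, which matters because data collection is scheduled to end in April 2018. The downside is precision. If the day-1 subset were about half the cohort, for example 26 of 27 responders (96.3%), the Wilson interval would be 81.7–99.3%, against 87.7–99.0% at 53/55. The subset also does not recover the missed patients, and it may differ in case mix from those enrolled later, so it should be shown beside the full CP result and not replace it.

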#### 9.4.1.2 During Treatment Documentation

Follow-up visits are scheduled by the physician per routine clinical practice. Likewise treatment, procedures and diagnostic methods will follow physicians' routine clinical practice.

---

##### Confidential Information

No use or disclose outside AbbVie is permitted without prior written authorization from AbbVie

The Netherlands v 1.4 (26 March 2018). Protocol based on AbbVie shell protocol version 3.0 (22 April 2015) Page 27 of 65

The following will be documented if available:

- Laboratory data

Key clinical chemistry

- ALT
- AST
- $\gamma$ -GT
- Total bilirubin
- Creatinine

Remarks

- including ULN
- including ULN,  
APRI and FIB-4 will be calculated
- creatinine clearance will be calculated

Key hematology

- Hb
- Platelets

Virology

- HCV RNA

quantitative/ qualitative HCV RNA PCR test, see 9.4.1.4

HIV-infected patients only

- CD 4 count
- HIV RNA

most recent assessment  
in copies/mL

- Concomitant medication, see 9.4.1.5
- Adherence to ABBVIE REGIMEN  $\pm$  RBV as established by interviewing the patient during regular visits
- Tolerability (sAEs and AEs, see 11.1.5) and pregnancies (see 11.1.6)
- Patient questionnaires see 9.4.1.6
- Treatment related health care resource utilization

### **9.4.1.3 Post-Treatment Documentation**

Follow-up visits are scheduled by the physician per routine clinical practice. Likewise treatment, procedures and diagnostic methods will follow physicians' routine clinical practice.

---

**Confidential Information**

**No use or disclose outside AbbVie is permitted without prior written authorization from AbbVie**

The Netherlands v 1.4 (26 March 2018). Protocol based on AbbVie shell protocol version 3.0 (22 April 2015) Page 28 of 65

The following will be documented:

- Laboratory data

Key clinical chemistry

- ALT
- AST
- $\gamma$ -GT
- Total bilirubin
- Albumin
- Creatinine

Remarks

including ULN  
including ULN,  
APRI and FIB-4, will be calculated

creatinine clearance will be calculated

Key hematology

- Hb
- Platelets
- Prothrombin time

or INR

Virology

- HCV RNA

quantitative/ qualitative HCV RNA PCR test, see 9.4.1.4

HIV-infected patients only

- CD 4 count
- HIV RNA

most recent assessment  
in copies/mL

- Tolerability (sAEs, see 11.1.4) and pregnancies (see 11.1.6)
- Patient questionnaires see 9.4.1.6

---

**Table 2 - Data Documentation Schedule**

Assessment/ Procedure (only available data to be collected; no diagnostic or monitoring procedures to be applied to the patients apart from those of routine clinical practice)	Baseline	Treatment Period			Post-treatment (PT) Period		
		On-treatment visits	Mid treatment visit for pts receiving 24 weeks of therapy	EoT b	Early PT visit	SVR 12 visit	SVR 24 visit
Informed Consent	X a						
Demographic information	X						
Relevant CHC disease characteristics	X						
Liver fibrosis stage	X						
CHC treatment history	X						
HCV genotype and subtype	X						
HCV RNA samples	X	X	X	X	X	X	X
Clinical chemistry and hematology	X	X	X	X	X	X	X
ABBVIE REGIMEN initiation documentation c	X						
ABBVIE REGIMEN adherence		X	X	X			
Concomitant medication	X	X	X	X			
Relevant medical history, co-morbidities	X						
SAE, AE and pregnancy reporting	X	X	X	X	X d	X e	X e
For patients receiving RBV: Evidence, in accordance with local label, that female patient or female partner of male patient is not pregnant	X						
Health care resource utilization	X	X	X	X			
Patient questionnaires – WPAI, EQ5D-5L	X			X		X	X

Abbreviations: EoT = End of Treatment (at Week 12 or 24 or at premature discontinuation),

PT = Post-Treatment

- a Written informed consent must be obtained before any data documentation in the eCRF
- b Patients who prematurely discontinue should return to the site to document EoT data
- c Healthcare professional documents the type of therapy that will be initiated (12 vs 24 wks, Paritaprevir/r – ombitasvir alone vs Paritaprevir/r – ombitasvir + dasabuvir, with or without Ribavirine depending on the genotype of the virus and disease status of the patient)
- d Tolerability documentation until PT week 4
- e Pregnancy reporting for patients treated with DAA +/- RBV (see 11.1.6)

Confidential Information

No use or disclose outside AbbVie is permitted without prior written authorization from AbbVie  
 The Netherlands v 1.4 (26 March 2018). Protocol based on AbbVie shell protocol version 3.0 (22 April 2015) Page 30 of 65

#### **9.4.1.4 HCV RNA Sample**

**HCV RNA sample** – the following needs to be documented:

- **Quantitative** HCV RNA by PCR test
  - Test name and result **in IU/mL**
  - Lower limit of detection (LLoD) **in IU/mL** and lower limit of quantification (LLoQ) **in IU/mL**
- **Qualitative** HCV RNA by PCR test
  - Test name and result **(positive/negative)**
  - LLoD **in IU/mL**

